**Table RHBX.6.2. Treatment Groups and Comparisons for Each Study Period and Analysis Population**

Study Period	Analysis Population	Treatment Group	Abbreviation	Comparison
Blinded Treatment Dosing Period (Period 2)	Intent-to-Treat (ITT) Population; Per-Protocol Set (PPS); Safety Population	Placebo Ixezumab 80 mg Q4W Ixezumab 80 mg Q2W Total Ixezumab Total Add the following treatment groups for analyses evaluating the impact of ixekizumab starting dose: Ixezumab 80 mg Q4W / 80 mg Starting Dose Ixezumab 80 mg Q4W / 160 mg Starting Dose Ixezumab 80 mg Q2W / 80 mg Starting Dose Ixezumab 80 mg Q2W / 160 mg Starting Dose Total Ixezumab / 80 mg Starting Dose Total Ixezumab / 160 mg Starting Dose	PBO IXE80Q4W IXE80Q2W Total IXE Total  IXE80Q4W/80S b IXE80Q4W/160S b IXE80Q2W/80S b IXE80Q2W/160S b Total IXE/80S b Total IXE/160S b	IXE80Q4W vs. PBO IXE80Q2W vs. PBO Overall a  IXE80Q4W/80S b vs. IXE80Q4W/160S b IXE80Q2W/80S b vs. IXE80Q2W/160S b Total IXE/80S b vs. Total IXE/160S b
Blinded Treatment Dosing Period (Period 2)	Inadequate Responder (IR) Population	Placebo IR / Ixezumab 80 mg Q2W Ixezumab 80 mg Q4W IR / Ixezumab 80 mg Q2W Ixezumab 80 mg Q2W IR / Ixezumab 80 mg Q2W Total Ixezumab IR / Ixezumab 80 mg Q2W Total IR / Ixezumab 80 mg Q2W	PBO IR/IXE80Q2W IXE80Q4W IR/IXE80Q2W IXE80Q2W IR/IXE80Q2W Total IXE IR/IXE80Q2W Total IR/IXE80Q2W	No Between-Group or Overall Comparisons
Post-Treatment Follow-Up Period (Period 3) c	Follow-Up Population	Placebo Ixezumab 80 mg Q4W Ixezumab 80 mg Q2W d Total Ixezumab Other Biologic e Total	PBO IXE80Q4W IXE80Q2W Total IXE Other e Total	No Between-Group or Overall Comparisons

Abbreviations: IXE80Q2W = ixekizumab 80 mg every 2 weeks; IXE80Q4W = ixekizumab 80 mg every 4 weeks; PBO = placebo; Q2W = every 2 weeks; Q4W = every 4 weeks.

- a Overall comparison will be conducted for demographics, historical illness, medical history, preexisting condition, and previous therapy. The between-group comparisons and the overall comparison will be conducted for concomitant therapy, compliance, disposition, and safety.
- b S = Starting dose, differences between starting dose groups and 95% confidence interval (CI) will be provided.
- c Treatment group refers to the treatment regimen that the patient received prior to entering Period 3.
- d Including patients who were on biologic rescue ixekizumab 80 mg Q2W before entering Period 3.
- e Including patients who have discontinued study treatment and were on other biologic therapy prior to entering Period 3.

Table of Contents

## **6.1.2. General Considerations for Analyses during the Blinded Treatment Dosing Period (Period 2)**

### **6.1.2.1. Intent-to-Treat Population and Safety Population**

Period 2 starts at the first injection of study treatment at Week 0 (Visit 2) and ends on the date of Week 52 (Visit 15) or the early termination visit (ETV; between Weeks 0 and 52). For patients who were deemed as inadequate responders by their investigators and were treated with biologic rescue of ixekizumab 80 mg Q2W, only data up to the time of initiation of biologic rescue of ixekizumab 80 mg Q2W will be included in the Period 2 analyses using the ITT and Safety Populations. These patients will be considered nonresponders to categorical assessment per the nonresponder imputation (NRI) method after initiation of biologic rescue with ixekizumab 80 mg Q2W. Data collected after biologic rescue therapy has started will be summarized separately for the IR Population (Section 6.1.2.2).

Baseline for ITT and Safety Populations will be defined as the last available value before the first injection for efficacy, health outcomes, and safety analyses. In most cases, this will be the measure recorded at Week 0 (Visit 2). For efficacy measures, if the patient does not take any injection, the last available value on or prior to randomization date will be used. Change from baseline (CFB) will be calculated as the visit value of interest minus the baseline value. For safety analyses using a baseline period, the baseline period is defined as the time from Visit 1 to the date/time of the first injection.

Comparisons between each initially randomized ixekizumab treatment group (80 mg Q2W or 80 mg Q4W) and initially randomized placebo will be performed for all analyses in Period 2.

The randomization to treatment groups is stratified by country and screening MRI/CRP status (positive MRI and elevated CRP; positive MRI and nonelevated CRP; negative MRI and elevated CRP) as described in Protocol Section 6.2. The countries will be categorized into geographic regions for analysis. Geographic regions are defined in Table RHBX.6.3. Unless otherwise specified, the statistical analysis models will adjust for geographic region and screening MRI/CRP status.

Screening MRI and CRP status included in all the analysis models for Period 2 is determined based on the MRI readings and central lab CRP values obtained at screening visit (Visit 1).

Unless otherwise specified, treatment groups of ixekizumab 80 mg Q2W and Q4W will be analyzed without regard to starting dose.

The primary analysis method for treatment comparisons of categorical efficacy and health outcomes variables at specific time points will be made using a logistic regression analysis with treatment, geographic region (Europe and non-Europe), and screening MRI/CRP status in the model using PROC Logistic with a Wald test. The odds ratio and 95% CIs will be reported; treatment difference and 95% CI will also be reported. Secondary analysis will be conducted using a Fisher's exact test. In the case when logistic regression model does not produce statistical results due to sparse data, Fisher's exact test will be used.

As a secondary analysis for the primary and major secondary categorical efficacy measures, a categorical, pseudo-likelihood based mixed-effects model of repeated measures (categorical mixed-effects model of repeated measures [MMRM]) estimating the percentage of patients achieving response across postbaseline visits may be used. The model will include treatment, geographic region, screening MRI/CRP status, visit, and treatment-by-visit as fixed factors. The binomial distribution and the logit link will be used. The restricted maximum likelihood (REML) will be used. An unstructured covariance matrix will be used to model the within-patient variance-covariance errors. The Kenward-Roger approximation will be used to estimate the denominator degrees of freedom. The Newton-Raphson with ridging optimization technique will be used to aid with convergence. The probability of response, the corresponding 2-sided 95% CI, and the p-value for treatment comparisons at Week 16 (Visit 8), Week 52 (Visit 15), and all other postbaseline visits will be reported.

If the unstructured covariance matrix results in a lack of convergence, the heterogeneous Toeplitz covariance structure, followed by the heterogeneous autoregressive covariance structure, followed by the compound symmetry will be used. This order is specified according to a decreasing number of covariance parameters in the structure. The sandwich estimator (Diggle et al. 1994) for the covariance estimation will be used by specifying the EMPIRICAL option in SAS PROC MIXED. When sandwich estimation is used, the Kenward-Roger approximation for denominator degrees of freedom cannot be used. Instead, DDFM= BETWITHIN option will be used to estimate denominator degrees of freedom.

The primary analyses for continuous efficacy and health outcomes variables will be made using MMRM. The primary analyses for MRI endpoints will be made using analysis of covariance (ANCOVA). A secondary analysis for continuous efficacy and health outcomes variables will be made using ANCOVA.

When the MMRM is used, the model will include treatment, geographic region, screening MRI/CRP status, baseline value, visit, baseline value-by-visit, and treatment-by-visit interaction as fixed factors (except for the analysis of CRP, see paragraph below). The covariance structure to model the within-patient errors will be unstructured. The REML will be used. The Kenward-Roger method will be used to estimate the denominator degrees of freedom. Type III tests for the least-squares (LS) means will be used for the statistical comparison; the 95% CI will also be reported. Treatment group comparisons with placebo at Week 16 (Visit 8), Week 52 (Visit 15) and all other visits will be reported. If the unstructured covariance matrix results in a lack of convergence, the similar approach specified above for categorical MMRM will be used.

For the analysis of mean change from baseline and ratio of postbaseline to baseline in CRP, MMRM model will include treatment, geographic region, screening MRI/CRP status, visit, and treatment-by-visit interaction as fixed factors. Note for the ratio of postbaseline to baseline in CRP, analysis will be performed on the natural log transformed ratio.

When the ANCOVA is used, the model will include treatment, geographic region, screening MRI/CRP status, and baseline value (except for the analysis of CRP, see paragraph below).

Type III sums of squares for the Least Squares (LS) means will be used for the statistical comparison; the 95% CI will also be reported.

For the analysis of mean change from baseline and ratio of postbaseline to baseline in CRP, ANCOVA model will include treatment, geographic region and screening MRI/CRP status. Note for the ratio of postbaseline to baseline in CRP, analysis will be performed on the natural log transformed ratio.

For the analysis of ASDAS disease activity states (ie, inactive, low, high, and very high disease states), the repeated measures proportional odds model will include treatment, geographic region, screening MRI/CRP status, visit, and treatment-by-visit interaction.

The impact of ixekizumab starting dose of 160 mg versus 80 mg on treatment response at Week 16 will be summarized and evaluated. Response rates in selected categorical variables (ASAS40/20, ASDAS<2.1, BASDAI50, ASDAS clinical important improvement, ASDAS major improvement) and LS mean change in selected continuous efficacy and health outcome measures (CRP, BASFI, BASDAI, spinal pain and SF-36 PCS) at Weeks 16 and 52 will be presented for patients randomized to ixekizumab Q2W or Q4W treatment regimen with ixekizumab 160 mg starting dose and with ixekizumab 80 mg starting dose.

For response rates, starting dose comparisons within ixekizumab Q2W or Q4W treatment regimens will be based on logistic regression model with treatment, starting dose, and treatment-by-starting-dose interaction (only ixekizumab Q2W and Q4W will be included in the analyses). Starting dose comparison combining ixekizumab Q2W and Q4W treatment regimens will be based on logistic regression model with only starting dose in the model.

For mean change analysis, starting dose comparisons within ixekizumab Q2W or Q4W treatment regimens will be based on MMRM model with treatment, starting dose, baseline value, visit, baseline value-by-visit, treatment-by-visit, treatment-by-starting dose, starting dose-by-visit, and treatment-by-starting dose-by-visit interactions as fixed factors. Starting dose comparison combining ixekizumab Q2W and Q4W treatment regimens will be based on MMRM model with starting dose, baseline value, visit, baseline value-by-visit, and starting dose-by-visit interaction as fixed factors. The differences in response rates and LS mean changes between starting doses and the corresponding 95% CI will be reported as well.

For variables that are not collected at each postbaseline visit, data may exist at visits where the variable was not scheduled to be collected, due to early discontinuation visits. In these situations, data from the early discontinuation visit that do not correspond to the planned collection schedule will be excluded from the MMRM and categorical MMRM analyses (Andersen and Millen 2013). However, the data will still be used in other analyses, including shift analyses, change from baseline to modified baseline observation carried forward (mBOCF) endpoint analyses, and other categorical analyses.

For selective efficacy measures, percent improvement will be calculated. For measures with higher scores indicating more severe, percent improvement will be calculated as  $100 \times (\text{baseline score} - \text{observed scores}) / \text{baseline score}$ ; for measures with lower scores indicating more severe,

percentage improvement will be calculated as  $100 \times (\text{observed scores} - \text{baseline score}) / \text{baseline score}$ . If a patient has experienced an improvement, this measure will be positive. If a patient has experienced a worsening, this measure will be negative.

Figures showing the proportion of patients achieving a categorical clinical response at each scheduled visit within each treatment group may be provided.

Fisher's exact test will be used for all adverse event (AE), baseline, discontinuation, and other categorical safety data. Continuous vital sign and laboratory values will be analyzed by an ANCOVA with treatment and baseline value in the model.

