## 6. Treatment

### 6.1. Treatments Administered

The Blinded Treatment Dosing Period (Period 2) involves a comparison of ixekizumab at 2 treatment regimens (80 mg Q2W and 80 mg Q4W) with placebo treatment. Each ixekizumab treatment regimen will include patients receiving an 80-mg or a 160-mg starting dose; patients will be randomized to a starting dose at a 1:1 ratio. All doses are administered via SC injection. [Table RHBX.2](#) shows the treatment regimens.

At baseline (Week 0), all patients will be randomized to a treatment group and receive 2 injections. Patients assigned to an ixekizumab treatment regimen with a 160-mg ixekizumab starting dose will receive 160-mg of ixekizumab as 2 SC injections (80 mg per SC injection). Patients assigned to an ixekizumab treatment regimen with an 80-mg starting dose will receive 80 mg of ixekizumab as 1 SC injection and 1 SC injection of placebo. Patients assigned to the placebo treatment group will receive 2 SC injections of placebo. After Week 0 and through Week 50, all patients will receive 1 injection every 2 weeks. Details of the patient treatment regimens are provided in [Table RHBX.2](#).

Beginning at Week 16 and up to Week 44, any patient, regardless of their original treatment group, may be identified by an investigator based on clinical judgment as an inadequate responder. At such time, changes in background therapy and/or addition of biologic rescue therapy (ixekizumab 80 mg Q2W) can be made at the discretion of the investigator, while remaining blinded to the original randomization treatment assignment. Changes in ongoing medications at that time can include changes in dose of NSAIDs or nonbiological disease-modifying antirheumatic drugs (DMARDs), including the introduction of new medications. The investigator may also decide to use biologic rescue of ixekizumab 80 mg Q2W with an 80-mg starting dose, which is a blinded decision as to whether the patient will be initiating ixekizumab, increasing the dose, or remaining on the same treatment regimen.

Investigators who believe a patient needs rescue ixekizumab 80 mg Q2W treatment will indicate such via interactive web-response system (IWRS), and these patients will receive ixekizumab 80 mg Q2W with an 80-mg starting dose. This option specifically means the following:

- Placebo inadequate responders will switch to ixekizumab 80 mg Q2W.
- Ixekizumab 80 mg Q4W inadequate responders will switch to ixekizumab 80 mg Q2W.

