**8.1.2.21. Imaging Used for Efficacy Measures and Disease Diagnosis**

**8.1.2.21.1. Imaging Used for Efficacy Measures and Disease Diagnosis**

For each patient, x-ray and MRI images will be collected according to the Schedule of Activities (Appendix 2) and Table RHBX.3 and will follow the study specific recommendations included in the site training materials for the study. The x-ray of the SIJ will be used to exclude patients with radiographic sacroiliitis as defined by the mNY criteria. MRI of the SIJ, collected at screening, Week 16, and Week 52 will generate objective data for the investigational drug on the anti-inflammatory effect as well as data on the evolution of structural changes in the SIJ. The screening x-ray of the spine will serve as baseline for later evaluation of change from baseline in structural progression in the long-term study (Study RHBV). All reading of x-ray and MRI images is done centrally.

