### **9.2.1. General Considerations for Analyses during the Blinded Treatment Dosing (Period 2)**

Comparisons between each ixekizumab regimen (80 mg Q2W or 80 mg Q4W) and placebo will be performed for all analyses in Period 2.

Period 2 starts at the first injection of study treatment at Week 0 (Visit 2) and ends at Week 52 (Visit 15) or the ETV (between Weeks 0 and 52). For patients who are deemed as inadequate responders by investigators after Week 16 and for whom the investigator indicates the need to use ixekizumab 80 mg Q2W, only data prior to the assignment of modified treatment by ixekizumab 80 mg Q2W will be included in the Period 2 primary analyses to avoid falsely ascribing benefit from the modified biologic treatment to the initially randomized treatment. For patients who are deemed as inadequate responders by investigators after Week 16 and for whom the treatment modifications are limited to concomitant medication only, all data from Period 2 will be included (from time of first injection of study treatment at Week 0 [Visit 2] up to and including Week 52 [Visit 15] or the ETV [between Weeks 0 and 52]).

Baseline will be defined as the last available value before the first injection for efficacy, health outcome, and safety analyses. In most cases, this will be the measure recorded at Week 0 (Visit 2). For efficacy measures, if the patient does not take any injection, the last available value on or prior to the randomization date will be used. Change from baseline will be calculated as the visit value of interest minus the baseline value. For safety analyses using a baseline period, the baseline period is defined as the time from Visit 1 to the date/time of the first injection.

The randomization to treatment groups is stratified by country and screening MRI/CRP status (positive MRI and elevated CRP; positive MRI and nonelevated CRP; negative MRI and elevated CRP) as described in Section 6.2. The countries will be categorized into geographic regions for analysis. Geographic regions will be defined in the SAP upon country finalization. Unless otherwise specified, the statistical analysis models will adjust for geographic region and screening MRI/CRP status.

Unless otherwise specified, treatment groups of ixekizumab 80 mg Q2W and 80 mg Q4W will be analyzed without regard to starting dose.

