##### 9.4.2.2.1. Period 2 (Blinded Treatment Dosing Period)

Unless otherwise specified, the other secondary analyses during Period 2 will be based on the ITT population.

Treatment comparisons in the proportion of patients achieving a categorical response at specified time point will be analyzed using the logistic regression model defined in Section 9.2.1. Missing data will be imputed using the NRI method described in Section 9.2.4.

For all continuous efficacy variables that are collected at repeated visits, treatment group comparisons will be analyzed using the MMRM model defined in Section 9.2.1. No imputation methods are applied to MMRM analysis. Additional analysis will be conducted using ANCOVA model defined in Section 9.2.1. Missing data will be imputed by the mBOCF method as described in Section 9.2.4.

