BASDAI	BASDAI change (Major Secondary) and % improvement from baseline (incl. 6 individual item and inflammation)	MMRM	ITT Population	IXE80Q2W & IXE80Q4W vs. placebo at Weeks 16 and 52 and all other postbaseline visits in Period 2	Major secondary efficacy analysis is MMRM mean change analysis for ITT Population comparing IXE80Q2W & IXE80Q4W vs. placebo at Weeks 16 and 52 (Section 6.10.2).
		ANCOVA with mBOCF	ITT Population	IXE80Q2W & IXE80Q4W vs. placebo at Weeks 16 and 52 and all other postbaseline visits in Period 2	Other secondary efficacy analyses (Section 6.10.4).
		Descriptive statistics	IR Population	Period 2 post initiation of biologic rescue of ixekizumab 80 mg Q2W	Exploratory analyses (Section 6.10.6.1)
BASFI	BASFI change from baseline and % improvement	MMRM	ITT Population	IXE80Q2W & IXE80Q4W vs. placebo at Weeks 16 and 52	Other secondary efficacy analyses (Section 6.10.4).
		MMRM	ITT Population	IXE80Q2W & IXE80Q4W vs. placebo at all other postbaseline visits in Period 2	Other secondary efficacy analyses (Section 6.10.4).

Measure	Variable	Analysis Method (Sections 6.1 and 6.3)	Population (Section 6.1.1)	Comparison/Time Point	Analysis Type
	from baseline	ANCOVA with mBOCF	ITT Population	IXE80Q2W & IXE80Q4W vs. placebo at Weeks 16 and 52 and all other postbaseline visits in Period 2	Other secondary efficacy analyses (Section 6.10.4).
		MMRM	ITT Population	IXE80Q2W & IXE80Q4W Starting Dose 160 mg and 80 mg during Period 2	Other secondary efficacy analyses (Section 6.10.4).
		Descriptive statistics	IR Population	Period 2 post initiation of biologic rescue of ixekizumab 80 mg Q2W	Exploratory analyses (Section 6.10.6.1)
SPARCC SIJ Score	SPARCC SIJ score change from baseline (major secondary)	ANCOVA with observed case analysis	ITT Population	IXE80Q2W & IXE80Q4W vs. placebo at Week 16	Major secondary efficacy analyses (Section 6.10.4).
		ANCOVA with observed case analysis	ITT Population	IXE80Q2W & IXE80Q4W vs. placebo at Week 52	Other secondary efficacy analyses (Section 6.10.4).
		ANCOVA with mBOCF	ITT Population	IXE80Q2W & IXE80Q4W vs. placebo at Weeks 16 and 52	Other secondary efficacy analyses (Section 6.10.4).
SPARCC SIJ Structural Score (SSS)	SPARCC SIJ SSS score change from baseline for each of the 4 features: fat metaplasia, bone erosion, backfill and anklyosis	ANCOVA with observed case analysis	ITT Population	IXE80Q2W & IXE80Q4W vs. placebo at Weeks 16 and 52	Other secondary efficacy analyses (Section 6.10.4).

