#### **6.10.4. Other Secondary Efficacy Analyses**

There will be no adjustment for multiple comparisons for other secondary efficacy analyses.

The other secondary efficacy analyses include:

- ASAS40: analyses other than primary analysis (Section 6.10.1), and additional analysis of the primary outcome (Section 6.10.3)
- ASAS20, ASAS5/6 and partial remission
- Change from baseline in individual components of the ASAS criteria (patient global, spinal pain, function [see BASFI below], inflammation [see BASDAI below], CRP [see CRP below], and spinal mobility (lateral spinal flexion) [see BASMI below])
- Change from baseline in BASDAI: analyses other than major secondary efficacy analysis, 6 individual items and inflammation (mean of Q5 and Q6 on BASDAI)
- BASDAI 50
- Change from baseline in ASDAS: analyses other than major secondary efficacy analysis (Section 6.10.2)
- ASDAS inactive disease (ASDAS<1.3)
- ASDAS disease activity states: inactive disease, low disease activity, high disease activity, very high disease activity, clinically important improvement and major improvement
- Change from baseline in CRP
- Change from baseline in BASFI
- Change from baseline in mobility (BASMI linear and individual components, chest expansion, occiput to wall distance)
- Change from baseline in SPARCC SIJ score: analyses other than major secondary efficacy analysis (Section 6.10.2)
- Change from baseline in SPARCC SIJ structural score (SSS) for each of the 4 features: fat metaplasia, bone erosion, backfill and ankyloses.

- Change from baseline in enthesitis score (MASES and SPARCC)
- Change from baseline in TJC and SJC scores
- Incidence of peripheral arthritis by TJC and SJC scores of 46/44 joints.
- Incidence rate of anterior uveitis
- Change from baseline in ASAS-NSAID score, Section [6.10.4.1](#).

Treatment comparisons of each ixekizumab treatment group and placebo at Weeks 16 and 52 and all other postbaseline visits during Period 2 for the ITT Population will be provided. For inadequate responders who were treated with biologic rescue of ixekizumab 80 mg Q2W, only data up to the time of initiation of biologic rescue of ixekizumab 80 mg Q2W will be included in these analysis.

The impact of ixekizumab starting doses will be evaluated for the selected categorical responses and mean change in selected continuous efficacy and health outcome measures at Weeks 16 and 52 and earlier time point as described in Section [6.1.2](#).

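### Week 52 SPARCC SIJ and SSS: the observed-case ANCOVA gives ixekizumab-rescued patients no weight despite their Week 16 scan, where the protocol prescribes MMRM and the SAP states no reason for departing

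*SAP*

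**What the plan says.** **Schedule.** Protocol 8.1.2.21.1 gives the MRI visits: "MRI of the SIJ, collected at screening, Week 16, and Week 52". The Schedule of Activities strongly recommends taking the Week 16 scan before Week 16 dosing. After Visit 8, an early-termination scan is required only if that visit falls on or after Visit 12.

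**Rescue.** Protocol 6.1: "Beginning at Week 16 and up to Week 44, any patient, regardless of their original treatment group, may be identified by an investigator" as an inadequate responder, and ixekizumab 80 mg Q2W may then be started. SAP 6.1.2.1 says that for patients so rescued "only data up to the time of initiation of biologic rescue of ixekizumab 80 mg Q2W will be included in the Period 2 analyses". SAP 6.10.4 repeats this for the other secondary efficacy analyses: "only data up to the time of initiation of biologic rescue of ixekizumab 80 mg Q2W will be included in these analysis". Inadequate responders without ixekizumab rescue are treated differently. Protocol 9.2.1 says that where "treatment modifications are limited to concomitant medication only, all data from Period 2 will be included".

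**Method in the SAP.** Section 6.1.2.1: "The primary analyses for MRI endpoints will be made using analysis of covariance (ANCOVA". Table RHBX.6.5 lists "ANCOVA with observed case analysis" first for SPARCC SIJ at Week 52 and for SSS at Weeks 16 and 52, followed by ANCOVA with mBOCF. All of these are labelled other secondary.

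**Method in the protocol.** Section 9.4.2.2.1, on other secondary endpoints: "For all continuous efficacy variables that are collected at repeated visits, treatment group comparisons will be analyzed using the MMRM model defined in Section 9.2.1". It makes no exception for MRI. Table RHBX.5 prescribes observed-case ANCOVA for one outcome only, SPARCC SIJ at Week 16.

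**The concern.** Observed-case ANCOVA at Week 52 is a single-visit model, so a patient without a usable Week 52 value carries no weight in it. Ixekizumab rescue follows the investigator's judgement of inadequate response. That is a post-randomisation event, and if the drug works it should be more frequent on placebo. The contrast is then between selected patients in each arm, and the selection may differ.

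The SAP avoids this for ASDAS, BASDAI and SF-36 PCS. Section 6.10.2 analyses them by MMRM with post-rescue data removed, so rescued patients still contribute their earlier visits. In the Week 52 observed-case MRI analysis they do not.

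The planned mBOCF analysis keeps rescued patients by carrying the Week 16 scan to Week 52. That assumes no change over 36 weeks, whereas Protocol 8.1.2.21.1 gives the evolution of structural change as one purpose of the scans. At stake is the interpretation of the 52-week imaging endpoints, not the confirmatory result.

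**Working it through.** **Plan figures.** The documents give no SD, effect size, between-visit correlation or rescue rate for MRI, so there is no MRI figure to reproduce. The stated power concerns ASAS40. Fisher's exact power for 46% against 18% with 100 per arm is 98.8%, which agrees with the stated 98% or so but does not bear on MRI.

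**Tracing one patient.** A patient has a scan at screening and at Week 16, starts ixekizumab rescue at, say, Week 24, and has a scan at Week 52.
- Week 16 SPARCC and SSS analyses: included.
- Week 52 observed-case ANCOVA: excluded, because the Week 52 scan is post-rescue.
- Week 52 ANCOVA with mBOCF: included, with the Week 16 value standing in for Week 52.
- Protocol MMRM over Weeks 16 and 52: included through the Week 16 value, with Week 52 treated as missing.

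**Illustrative size.** Everything here except 100 per arm is an assumption: true difference -3.0 at both visits, SD 6, Week 16 to Week 52 correlation ρ = 0.7, and rescue when a clinical status variable, correlated r with MRI at both visits, exceeds an arm-specific threshold.

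With a fraction f rescued, those remaining have mean clinical status -λ, where λ = φ(z)/(1 - f) and z is the standard normal quantile at 1 - f. Then, approximately:
- observed-case estimate = -3.0 + r × 6 × (λ placebo - λ ixekizumab)
- two-visit likelihood estimate = -3.0 + (1 - ρ) × r × 6 × (λ placebo - λ ixekizumab)
- observed-case variance per arm = 36 / [100(1 - f)]; the two-visit variance is this times (1 - ρ²f)

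For 50%/30% rescue, λ is 0.798 and 0.497, a difference of 0.301. With r = 0.4 the observed-case estimate is -3.0 + 0.4 × 6 × 0.301 = -2.28, and the two-visit estimate is -3.0 + 0.3 × 0.72 = -2.78.

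| Rescued, placebo/ixekizumab | λ difference | Observed-case, r = 0.2 / 0.4 | Two-visit, r = 0.2 / 0.4 | SE, observed-case / two-visit | SE reduction |
|---|---|---|---|---|---|
| 20% / 10% | 0.155 | -2.81 / -2.63 | -2.94 / -2.89 | 0.92 / 0.89 | 3.8% |
| 30% / 30% | 0 | -3.00 / -3.00 | -3.00 / -3.00 | 1.01 / 0.94 | 7.6% |
| 50% / 30% | 0.301 | -2.64 / -2.28 | -2.89 / -2.78 | 1.11 / 0.99 | 10.8% |
| 60% / 40% | 0.322 | -2.61 / -2.23 | -2.88 / -2.77 | 1.22 / 1.06 | 13.7% |

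With r = 0 every estimate is -3.0 and only the standard errors differ. Simulation of the same set-up, including with baseline adjustment, agrees: two-visit estimates about -3.0 to -2.7, and SE gains of 1% to 4% at 20%/10% and 7% to 14% at the higher rates.

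**A different mechanism.** If rescue depends directly on the Week 16 MRI change (correlation 0.6, log-odds 1 per SD), simulation gives observed-case -2.38 against MMRM -2.92 at 40%/20% rescue, and -2.16 against -2.99 at 60%/30%. This favours MMRM, because the cause of missingness is in the model.

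**mBOCF.** When the true difference is the same at both visits, carrying Week 16 forward is nearly unbiased (-2.95 to -3.09 in those simulations). If the difference instead grows from -1.5 at Week 16 to -3.0 at Week 52 with placebo flat, it gives 0.7 × (-3.0) + 0.3 × (-1.5) = -2.55 with 30% of the ixekizumab arm rescued, and 0.6 × (-3.0) + 0.4 × (-1.5) = -2.4 with 40% rescued.

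**The case against.** The case for leaving the plan alone has real content.

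- **Protocol latitude.** Section 9.4.2.2 leaves details of these analyses to the SAP, and 9.2 requires an amendment only for a principal feature. A reader might infer a protocol breach, and the documents do not support that. What stands is narrower: 9.4.2.2.1 names the method, 9.2 asks for other changes to be justified in the clinical study report, and the SAP revision history records updated MRI analyses without a reason.
- **Possible convention.** WPAI-SpA and EQ-5D, also measured after baseline only at Weeks 16 and 52, likewise get ANCOVA without MMRM. That may explain the choice. However, those analyses use mBOCF, which keeps rescued patients.
- **Who is excluded.** A reader might infer that only patients never judged inadequate responders remain. That is wrong: those with concomitant-medication changes alone stay in.
- **Scans discarded.** A reader might also infer that rescued patients' Week 16 scans are thrown away. They are used in the Week 16 analyses and in mBOCF, and are missing only from the Week 52 observed-case analysis.
- **No confirmatory effect.** Only Week 16 SPARCC is in the testing schemes of SAP 6.5, and rescue does not remove its scans. When placebo is rescued more, the bias works against the drug.
- **MMRM is not a cure.** Rescue is driven by symptoms, which an MRI-only model does not contain, so some bias remains. MMRM also targets the effect had rescue not occurred. Both points stand. Observed-case ANCOVA, though, needs a stronger assumption about the same missing values.

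**Conclusion.** The point holds for Week 52 change in SPARCC SIJ and the four SSS features. The analysis listed first drops every ixekizumab-rescued patient, although the protocol's own model would use their pre-rescue Week 16 scans, and no reason is stated.

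It is tempting to say that the result will be biased, but the documents do not establish that. Bias needs rescue that both differs by arm and is related to MRI. At equal rescue, or with no relation, only precision is lost. On the assumed inputs the observed-case shift is 0.2 to 0.8 on a true -3.0, at most about 0.6 of a standard error (0.77 / 1.22), and the two-visit model removes about 70% of it (the assumed ρ). Real rescue rates and correlations could move this either way, and SSS has no separate calculation.

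This is a worthwhile correction to secondary imaging analyses. Type I error control and the Week 16 SPARCC test are unaffected.

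**What to change.** For Week 52 change in SPARCC SIJ and each SSS feature, make the lead analysis the MMRM of Protocol 9.2.1 with Weeks 16 and 52 as visits. Include every patient with a baseline and at least one pre-rescue postbaseline MRI. Keep observed-case ANCOVA and mBOCF ANCOVA as supportive, and note beside mBOCF that it assumes no change after Week 16 in rescued patients. Leave the alpha-controlled Week 16 SPARCC analysis as it is. If the sponsor prefers ANCOVA, the SAP should say why 9.4.2.2.1 is not followed and report by arm how many patients rescue removes.

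The cost is a change to SAP wording and a few model runs on data already collected. The downside is reliance on missing-at-random given the observed MRI values, the same kind of assumption that the plan's other MMRM analyses make.
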